8.1.5.1.4. Relative Bioavailability and Food Effect

Part 3

The following pharmacokinetic statistical analyses will only be performed if sufficient data is available (i.e. if participants have well defined plasma profiles).

Endpoint / Variables

 • Log-transformed $AUC(0-24)$, $AUC(0-\infty)$ (or $AUC(0-t_{last})$ if $AUC(0-\infty)$ cannot be derived), and C_{max}
Model Specification

 • $AUC(0-24)$, $AUC(0-\infty)$ and C_{max} will be separately analysed using a mixed effects models. In each model the dependent variable will be the log-transformed PK parameter of interest ($AUC(0-\infty)$ or C_{max}). • For the RBA model the primary comparison will be Tablet vs. PiB (B vs. A), the independent variables will include a fixed effect for treatment (PiB or Tablet) and period, and a random effect for participant. • For the Food effect model the primary comparison will be Tablet Fed vs. Tablet Fasted (B vs. C), the independent variables will include a fixed effect for fasting status (fed vs. fasted) and period, and a random effect for participant $\log(Pk\ Parameter) = \beta_0 + \beta_1 Treatment + \beta_2 Period + \gamma_i Subject$

Model Checking & Diagnostics

 • A compound symmetry covariance structure for the R matrix will be used by specifying “type=CS” on the RANDOM line • In the event that this model fails to converge, alternative correlation structures may be considered such as CSH. • The Kenward and Roger method for approximating the denominator degrees of freedom and correcting for bias in the estimated variance-covariance of the fixed effects will be used. • Normality assumptions underlying the model used for analysis will be examined by obtaining a normal probability plot of the residuals and a plot of the residuals versus the fitted values (i.e. checking the normality assumption and constant variance assumption of the model respectively) to gain confidence that the model assumptions are reasonable. • If there are any departures from the distributional assumptions, alternative models will be explored using appropriate transformed data.
Model Results Presentation

 • The estimated difference and CI obtained on the log scale will be exponentiated to provide an estimate of the fed to fasted or tablet to PiB ratio and its associated 90% CI. Estimates of within-subject variability (%CVw) will also be provided (%CVw=SQRT(exp(MSE) – 1)×100). %CVw represents a pooled measure of within-subject variability across all treatments. • Comparative plots of individual PK parameters will be generated by treatment on linear and semi-logarithmic scales. • Plots of adjusted geometric mean ratio of test to reference treatment together with 90% confidence intervals will be produced. • Listing of individual PK parameter ratios will be generated. • Supportive SAS output from statistical analysis will be generated.
Subgroup Analyses

 • Not Applicable.
Sensitivity and Supportive Analyses

 • Not Applicable.

8.2. Exploratory Pharmacokinetic Analyses

Exploratory analyses to assess the exposure response relationship between VH3739937 and QTcF following single and repeated administration (Part 1 & 2) will be conducted. Linear regression models using exposure as the independent variable and change from baseline in QTcF as the outcome variable will be run separately for Part 1 and 2.

$$y_{\delta QTcF} = \beta_0 + \beta_1 X_{Concentration}$$

The model estimates $\hat{\beta}_0$ and $\hat{\beta}_1$ and their 95% confidence intervals will be reported, and the regression line will be overlayed on the plot of the comparison of change in QTcF and concentration.

**9. POPULATION PHARMACOKINETIC (POPPK)
ANALYSES**

The population PK analysis and pharmacodynamic analyses are exploratory endpoints that will be performed under a separate RAP and reported separately from the main clinical study report (CSR).

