Procedure	Pre-Treatment Days		Treatment Days			In House Post Treatment Days					Notes
	-2	-1	1	2, 4, 6, 8, 10, 12, 14	3, 5, 7, 9, 11, 13	15 (24 h)	16 (48 h)	17 (72 h)	18 (96 h)	19 (120 h)	
Admission to Unit	X										In a pandemic situation see Appendix 7 .
Discharge from Unit										X	In a pandemic situation see Appendix 7
Brief Physical Exam		X		X (Day 6)		X				X	Brief physical examinations may be made full and laboratory procedures may be repeated if needed at the discretion of the PI.
CSSRs				X (Day 12)						X	
Weight, BMI		X								X	
Vital signs		X	X	X			X		X	X	Vital signs to be performed pre-dose. Temperature will be monitored every day during study participation. For further detail, see Section 8.1.2
12-lead safety ECGs		X	X	X	X (Day 3)	X	X	X	X	X	ECG should be performed pre-dose on dosing days. ECG timepoints may be reduced in subsequent dosing groups. For further detail, see Section 8.1.4
Continuous ECG (full time matched baseline on Day-1)		X	X	X (Day 2 end of 24 h collection from Day 1 and Day 14)		X (end of 24 h collection from Day 14)					Continuous ECG monitoring from Day -1 to 24 h post dose on Day 1 and 14. ECG data extraction will coincide with PK sampling schedule at pre-dose, 1, 2, 3, 4, 5, 6, 7, 8, 9, 10, 12, 16 and 24 h post dose on Days 1,

Procedure	Pre-Treatment Days		Treatment Days			In House Post Treatment Days					Notes
	-2	-1	1	2, 4, 6, 8, 10, 12, 14	3, 5, 7, 9, 11, 13	15 (24 h)	16 (48 h)	17 (72 h)	18 (96 h)	19 (120 h)	
											Hours (h) relate to PK sampling post last dose
Testing for SARS CoV-2	X			X (Day 14)	X (Day 7)					X	2, 14 and 15 and on corresponding timepoints on Day -1. For further detail, see Section 8.1.4
Drug/alcohol/cotinine screen	X										An additional SARS-CoV-2 test will be performed approximately one week prior to admission to the unit. Weekly SARS-CoV-2 testing is required while in the unit (Days 7 and 14) and on discharge (Day 19). An approved molecular test (PCR) will be used. For further detail, see Appendix 7 and Section 8.1.3.
Haematology/Chemistry / Urine tests		X	X	X			X		X	X	For further detail, see Appendix 2
Pregnancy Test	X										Female participants only. For further detail see Appendix 2
VH3739937 Dose Administration			X	X	X						Once-daily oral dose from Day 1 to Day 14. Randomization to occur on Day 1 prior to dosing.
Meals	Per site usual practice										For meal instructions prior to dose, see Section 5.3.1

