Haematology/Chemistry/Urine tests	X	X	X	For further detail, see Appendix 2
Plasma PK Sampling	X	X	X	About 2 mL of blood will be collected at each visit.
Urine PK Sampling	X	X	X	Fresh spot urine sample collection at each visit. Please see SRM for further detail.
SAE/AE Review	<=====>			All SAEs will be collected from screening until follow up visit; All AEs will be collected from first dose until follow up visit
Concomitant Medication Review	<=====>			

Table 4 Part 2 MAD Cohort 5: Study Intervention (Day-2 to Day 23) – In Unit Duration

Procedure	Pre-Treatment Days		Treatment Days			In House Post Treatment Days					Notes
	-2	-1	1	2, 4, 6, 8, 10, 12, 14, 16, 18	3, 5, 7, 9, 11, 13, 15, 17	19 (24 h)	20 (48 h)	21 (72 h)	22 (96 h)	23 (120 h)	
Admission to Unit	X										Hours (h) relate to PK sampling post last dose
Discharge from Unit										X	In a pandemic situation see Appendix 7
Brief Physical Exam		X		X (Day 18)	X (Day 9)					X	Brief physical examinations may be made full and laboratory procedures may be repeated if needed at the discretion of the PI.
CSSRs				X (Day 18)	X (Day 9)					X	
Weight, BMI		X								X	
Vital signs		X	X	X	X (Days 15 and 17)		X		X	X	Vital signs to be performed pre-dose. Temperature will be monitored every day during study participation. For further detail, see Section 8.1.2
12-lead safety ECGs		X	X	X	X (Days 3, 15 and 17)	X	X	X	X	X	ECG should be performed pre-dose on dosing days. ECG timepoints may be reduced in subsequent dosing groups. For further detail, see Section 8.1.4
Continuous ECG (full time matched baseline on Day-1)		X	X	X (Day 2 - end of 24 h collection from Day 1 and Day 14)	X (Day 15 - end of 24 h collection from Day 14)						Continuous ECG monitoring from Day -1 to 24 h post dose on Day 1 and 14. ECG data extraction will coincide with PK sampling schedule at pre-dose, 1, 2, 3, 4, 5, 6, 7, 8, 9, 10, 12, 16 and 24 h post dose on Days 1, 2, 14 and

Procedure	Pre-Treatment Days		Treatment Days			In House Post Treatment Days					Notes
	-2	-1	1	2, 4, 6, 8, 10, 12, 14, 16, 18	3, 5, 7, 9, 11, 13, 15, 17	19 (24 h)	20 (48 h)	21 (72 h)	22 (96 h)	23 (120 h)	
											15 and on corresponding timepoints on Day -1. For further detail, see Section 8.1.4

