All participants will have a screening visit within 28 days prior to first dose and a follow-up visit approximately 28 days after the last dose. All dosing will be conducted in a hospital based inpatient clinical trial unit. Study participants will be confined to the clinic from Day -2 until discharge. Additional outpatient visits will be required for all study parts. Flexibility of visit scheduling may be required if a pandemic situation applies (see Appendix 7). Otherwise, study assessments will be performed as indicated in the SoA presented in this protocol.

A summary of the overall study design, including proposed doses, sample size, and order, is presented in Figure 3 and Figure 4 below.

Figure 3 Phase 1 Study in Healthy Participants using planned doses of VH3739937 Part 1 and Part 2

A=Active; P=Placebo

QD = once daily; QW = once weekly

*= Period 4 may include participants from both Cohorts 1 and 2

Highlighted cohorts and treatment periods denotes completed

The doses shown in [Figure 3](#) above are intended to demonstrate general concepts relating to factors of escalation. The modelling and simulation implemented using the data currently available following oral administration of a suspension formulation in the fed state indicated the predicted efficacious dose for the daily dose is 25 mg and the weekly dose is 500 mg. Due to the observed half-life of ~90 h, the anticipated accumulation ratio following repeated daily and weekly doses is ~6-fold and 1.3-fold, respectively. Dosing will be conducted in accordance with safety and PK stopping criteria (Section [7.1.4](#)).

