The SAD portion of the study will be conducted in an interlocking fashion with two separate cohorts each of approximately 9 healthy participants. Each of these two cohorts may contain a minimum of three escalating doses of VH3739937 through to 640 mg. An additional 800 mg dose will be evaluated as this was indicated following review of safety and PK data from participants dosed up to 640 mg. The interlocking design shown in [Figure 3](#) and the randomization sequence in [Table 7](#) will allow the 9 participants in each cohort to potentially receive one of the lower and one of the higher doses of VH3739937. Participants in Cohort 1 and Cohort 2 will follow the same randomization strategy with alternating ascending doses ([Table 7](#)). In each escalating dose period, 6 participants will be randomized to receive VH3739937 and 3 participants will be randomized to receive placebo. Participants in either Cohort will be assigned to one of the three treatment sequences, and each participant will receive placebo at least once. When the 800 mg dose is evaluated, 6 participants from both Cohorts 1 and 2 will be randomized to receive VH3739937 and 3 participants will be randomized to receive placebo, independent of which prior doses they received.

Details of the starting dose and dose escalation can be found in Section 4.3

Table 7 Description of treatment sequences in Cohort 1 and Cohort 2 Periods 1, 2, and 3

Cohort 1	Period 1	Period 2	Period 3
Sequence 1	Placebo	Dose 3	Dose 5
Sequence 2	Dose 1	Placebo	Dose 5
Sequence 3	Dose 1	Dose 3	Placebo

Cohort 2	Period 1	Period 2	Period 3
Sequence 1	Placebo	Dose 4	Dose 6
Sequence 2	Dose 2	Placebo	Dose 6
Sequence 3	Dose 2	Dose 4	Placebo

For Part 1, 24-hour continuous Holter/ ECG recordings will be collected on the day before dosing (Day -1), and Day 1 for extraction of ECGs paired with PK sampling.

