8.1.4.1. Cardiodynamic assessment (ECGs extracted from Holter recordings)

The frequency of ECG data in the SAD and MAD arises from emerging literature suggesting frequent QT evaluation early in development may mitigate the need for a formal TQT study [Darlo, 2014]. ECGs will be extracted as shown in the [SoA](#) from the SAD and the MAD component of the study. Should clinical development of VH3739937 continue, an exploratory objective of this study is to assess the exposure-response relationship between VH3739937 and QTcF following single and repeat dose administration.

The 12-lead Holter and ECG equipment will be used and may be supplied and supported by eREsearchTechnology, Inc. (ERT) or the contract research organization (CRO). All ECG data will be collected using a Global Instrumentation (Manlius, NY, USA) M12R ECG continuous 12 lead digital recorder. The continuous 12-lead digital ECG data will be stored onto SD memory cards. ECGs to be used in the analyses will be selected by pre-determined time points as defined in the [SoA](#), and will be read centrally by ERT, Inc.

The following principals will be followed in ERT's core laboratory:

- ECG analysts are blinded to the subject, visit and treatment allocation
- Baseline and on-treatment ECGs for a particular subject will be over-read on the same lead and will be analyzed by the same reader.
- The primary analysis lead is lead II. If lead II is not analyzable, then primary lead of analysis will be changed to another lead for the entire subject data set.

The following is a brief description of ECG analysis methods utilized by ERT's core laboratory.

TQT Plus ECG Extraction Technique

Ten 14-second digital 12-lead ECG tracings will be extracted from the continuous Holter recordings using the 'TQT Plus method', a computer-assisted and statistical process utilized by ERT, Inc. The method enables extraction of ECGs with the lowest heart rate (HR) variability and noise within the protocol-specified extraction time window (e.g., the HR and QT changes from beat-to-beat in the range of <10%). At each protocol-specified timepoint, 10 ECG replicates will be extracted from a 5-minute "ECG window" (typically, the last 5 minutes of the 15-minute period when the subject is maintained in a supine or semi-recumbent quiet position).

High-Precision QT Analysis

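### SAP 8.2 regresses change in QTcF on concentration over many readings per participant without allowing for their correlation, so the reported 95% intervals are expected to be too narrow (exploratory analysis)

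*SAP*

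**What the plan says.** SAP 8.2 plans the exposure-response analysis of QTcF: "Linear regression models using exposure as the independent variable and change from baseline in QTcF as the outcome variable will be run separately" for Parts 1 and 2. The equation has an intercept and a concentration slope and nothing else. Of the two estimates it says "and their 95% confidence intervals will be reported, and the regression line will be overlayed" on the scatter plot. Figures 4.16 and 4.17 in SAP Appendix 10 show that the data are individual, time-matched pairs, and the note to Figure 4.16 also asks for a 95% CI around the line.

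Neither place names the ECG source. The protocol points to the Holter recordings. Section 4.1 describes recordings on Day -1 and "Day 1 for extraction of ECGs paired with PK sampling" in Part 1, with a similar arrangement for Cohorts 3 to 5, and section 8.1.4 says safety-ECG parameters are generally not collected. For Cohorts 3 to 5 the Schedule of Activities (Tables 3 and 4) says "ECG data extraction will coincide with PK sampling schedule at pre-dose" and then lists 13 post-dose times to 24 h for the Day 1 and Day 14 doses, "and on corresponding timepoints on Day -1". In Part 1 (Protocol Table 7) each participant has two active periods and one placebo period.

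Elsewhere the SAP does model repeated data. The Part 1 power model, the accumulation model, the steady-state model and the relative bioavailability and food-effect models (SAP 8.1.5.1.1 to 8.1.5.1.4) all carry a participant random effect.

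**The concern.** Ordinary least squares treats every pair as independent. In Part 2, 21 active participants with 28 pairs each give 21 × 28 = 588 rows and 588 − 2 = 586 residual degrees of freedom, although only 21 people stand behind them. Readings from one person on one day are likely to share a QTcF shift.

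Repeated readings do not always narrow a slope interval. If concentration varied only within participants and only intercepts differed, the interval could even be conservative. This design is different. Dose differs between participants and periods, and "Due to the observed half-life of ~90 h" (Protocol 4.1) concentration is fairly flat over 24 h once absorbed. Exposure therefore varies at the same level at which QTcF shifts are shared. Clustering alone does not bias the slope or intercept, but it overstates their precision, and the interval is the only measure of uncertainty that 8.2 reports.

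**Working it through.** The plan gives no standard error or precision for this analysis, so there is no figure to reproduce. The planned sampling was simulated with a true slope of zero and the 8.2 model fitted as written.

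**Inputs from the documents.** Half-life about 90 h. Part 2: 7 active and 3 placebo in each of Cohorts 3 to 5, Days 1 and 14, concentrations scaled to the Table 11 median Cmax (0.968 µg/mL at 50 mg, 1.72 µg/mL at 100 mg; 25 mg taken as half of 50 mg). Part 1: 18 participants on the Table 7 sequences, scaled to the predicted 1.60 µg/mL at 800 mg, with the 800 mg period left out.

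**Assumptions.** One compartment, ka 0.5/h, exposure CV 30% (plus 15% between periods in Part 1), 14 points over 0-24 h per day or period, and a within-participant QTcF correlation varied from 0 to 0.60. There were 1500 replicates per setting (Monte Carlo error 0.6-1.3 points).

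**Where concentration varies.** The share of its variance lying between participant-days (Part 2) or participant-periods (Part 1) is 99% and 83-86%.

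**Coverage of the nominal 95% slope interval (%), and the ratio of actual to reported standard error:**

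| Correlation | Part 2 active | Part 2 with placebo | Part 1 active | Part 1 with placebo | SE ratio |
|---|---|---|---|---|---|
| 0 | 95.1 | 95.3 | 95.5 | 94.7 | about 1.0 |
| 0.05 | 90.3 | 87.1 | 90.9 | 92.0 | 1.1-1.3 |
| 0.10 | 85.7 | 82.7 | 85.1 | 87.7 | 1.3-1.5 |
| 0.20 | 76.9 | 71.5 | 76.5 | 81.5 | 1.5-1.8 |
| 0.30 | 72.1 | 63.3 | 73.2 | 73.9 | 1.7-2.2 |
| 0.60 | 58.2 | 50.3 | 58.5 | 62.6 | 2.2-2.9 |

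**Consistency check.** If the standard error is too small by a factor r, coverage is about 2Φ(1.96/r) − 1. For r = 1.5 this is 2Φ(1.307) − 1 = 0.81, and for r = 1.8 it is 2Φ(1.089) − 1 = 0.72, against 71.5-81.5% in the 0.20 row. For r = 2.2 and 2.9 it is 0.63 and 0.50, against 50.3-62.6% in the 0.60 row.

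**Different assumptions.** A second simulation used ka 0.4/h, about 35% variability and post-dose readings, included the 800 mg period, and split the correlation into a participant share plus a day or period share. At 0.1 + 0.05, slope coverage was 75-79%. At 0.2 + 0.1 it was 62-69% for the slope and 50-57% for the intercept. Halving the readings at 0.2 + 0.1, active participants only, still gave 77-80% for the slope.

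**Effect of the baseline.** With a Day -1 time-matched baseline, slope coverage is 94-97% if there are no whole-day QTcF shifts. It falls to 87-91%, 82-85% and 68-77% if such shifts make up 5%, 10% and 20% of reading variance. With a Day 1 pre-dose baseline it is 53-62% even without day shifts, but that assumes a baseline no more precise than a single later point.

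**Remedies.**
- Participant-clustered standard errors (t, n − 1 df): 90-94% in every setting.
- Participant random intercept only: about 96% when the correlation is at participant level alone, 63-85% once a day or period share of 0.1-0.2 is present.
- Participant plus day or period effect: 94-99%. If slopes also vary between participants (assumed SD 3 ms per µg/mL, total SD 8 ms, shares 0.2 + 0.1, 150 replicates), this falls to about 93% in Part 2 and 87% in Part 1; with SD 6 it falls to 81% and 75%.

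**The case against.** The strongest reply is that little depends on this analysis. It is exploratory, Protocol 9.1 tests no hypothesis, 8.2 sets no threshold, and no PK table is listed for the regression, only two scatter plots. Protocol 9.4.5 makes PK/PD work conditional on development continuing, and SAP 9 and 10 send such work to separate reporting. The line may be meant as a descriptive overlay. This stands as a limit on importance. It does not remove the point, because 8.2 says the analysis will be done and commits to 95% intervals, and both figures are listed deliverables.

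A second reply also stands in part. The size of the effect is assumed, and with a Day -1 time-matched baseline and no day shifts plain regression is adequate for the slope. The Holter source, and with it the count of 28, is inferred. Repeated readings exist in either ECG stream, so the direction does not depend on that inference.

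Two stronger readings are tempting. A reader might infer that the baselines contradict each other, since SAP 5.2 averages a Day 1 pre-dose triplicate while the Schedule of Activities has "Continuous ECG (full time matched baseline on Day-1". The SAP rule describes a triplicate ECG and allows exceptions; the schedule label belongs to the continuous recording, where up to "10 ECG replicates will be extracted from a 5-minute" window. These can be two ECG streams, each with its own baseline. What is missing is a statement of which one 8.2 uses. A reader might also infer that a faulty interval would undermine a case for avoiding a thorough QT study. Protocol 8.1.4.1 gives that as background for the frequent ECGs, but 8.2 states no such use.

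**Conclusion.** The concern holds for direction. As written, the 8.2 intervals ignore within-participant correlation in a design where exposure varies mainly between participants, days and periods. At every non-zero correlation tried they were too narrow, in both parts and with or without placebo data.

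The size is not known. It depends on a QTcF correlation that the documents do not give, and on the baseline. The table is a range under stated assumptions, so the documents do not support a claim that the intervals will cover only about half the time. Nor do they support a claim that the estimates are biased by clustering. The consequence is limited to overstated precision in an exploratory slope and intercept.

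**What to change.** In SAP 8.2 and for Figures 4.16 and 4.17, choose one of the following:

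1. Keep the regression and compute the intervals with participant-clustered standard errors, using a t reference and a small-sample correction.
2. Fit a mixed model with a participant random intercept, a random slope where estimable, and a participant-by-day (Part 2) or participant-by-period (Part 1) effect. A participant intercept alone is not enough.
3. Present the line as descriptive and delete the 95% intervals from 8.2 and from the figures.

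The cost is SAP wording and minor programming, with no new data. The intervals will be wider, and clustered standard errors with this few participants still cover slightly under 95% (about 90-94% in the simulation). The third option costs one sentence.

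As secondary clarifications, state which ECG stream and which baseline 8.2 uses, and align 8.2 with SAP 9 and 10 and Protocol 9.4.5 on whether and where the analysis is reported.
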